### **9.3 Demographic and Baseline Characteristics**

Demographic variables include: age, sex, ethnicity, and race. Age is provided by the IVR system and not derived.

Other characteristics include: height, weight, and body mass index (BMI).

Baseline disease characteristics to be summarized are the weekly average Abdominal Pain Intensity, weekly average stool frequency, and weekly proportion (as %) of days with at least one stool of Type 6 or 7 on the Bristol Stool Chart.

Descriptive statistics will be presented for age, height, weight, BMI, and other continuous variables. Frequency counts and percentages will be presented for sex, ethnicity and race. Age will also be summarized by groups ( $\leq 44$  years, 45 – 64 years, and  $\geq 65$  years). The denominator for percentages will be the number of subjects in the IBS subtype and treatment for the analysis set. Demographic variables and characteristics will be summarized for the Safety, Full, and the Efficacy Evaluable Analysis Sets.

### **9.4 Medical History**

Medical History verbatim terms in the eCRFs will be coded using the Medical Dictionary for Regulatory Activities (MedDRA). Medical History will be summarized by primary MedDRA System Organ Class (SOC) and preferred term (PT) within the SOC. Subjects will be counted once at each level.

### **9.5 Prior and Concomitant Medications**

Prior and concomitant medication verbatim terms in the eCRFs will be mapped to Anatomical/Therapeutic/Chemical (ATC) class and Preferred Names using the WHO Drug Dictionary (WHODD) Global.

Prior medications are those medications that started before the initial dose of study drug and end prior to the first dose. Concomitant medications are those medications that started on or after the date of the initial dose of study drug or medications that started before the initial dose of study drug and continued during the treatment period.

Prior and concomitant medications will be summarized for each treatment by WHO ATC class level 3 and preferred name. These summaries will present the number and percentage of subjects using each medication.

Subjects may have more than 1 medication per ATC class and preferred name. At each level of subject summarization, a subject is counted once if he/she reported 1 or more medications at that level. Each summary will be ordered by descending order of incidence of ATC class and descending incidence of preferred name within each ATC class as observed in all subjects. Ties will be broken alphabetically.

Changes to concomitant medications, including new medications and stopping of current medications are recorded in the eCOA device. This data will be entered in the eCRF.

## 9.6 Concomitant Procedures

Concomitant procedures recorded in the eCRF will be listed only.

## 10. EFFICACY ANALYSES

The primary efficacy analysis will be based on the FAS. Additional supportive efficacy analyses will be performed using the Efficacy Evaluable Set.

### 10.1 Efficacy Endpoints

The efficacy endpoints in this study are derived from daily eCOA diary entries and from questionnaires administered during the Week 4 and Week 8 (EOT) visits.

#### 10.1.1 Primary Efficacy Endpoint

The primary efficacy endpoint is whether the subject is an overall responder. The definition of an overall responder is IBS subtype specific and consists of two components.

For both IBS subtypes, the first component of overall response is the weekly average of Abdominal Pain Intensity (0-10, 0=none, 10=worst possible pain) over the past 24 hours. Improvement for the week is defined as a decrease of at least 30% compared with baseline.

For the IBS-C subtype, the second component of overall response is the stool frequency per week. Improvement is defined as an increase of 1 or more complete spontaneous bowel movements (CSBMs) per week compared with baseline. The number of bowel movements is recorded once per day in the eCOA device, including zeroes.

For the IBS-D subtype, the second component of overall response is the proportion of days per week with at least one stool with a consistency of Type 6 or 7 on the Bristol Stool Chart. Improvement is defined as a decrease in the proportion of at least 50% compared with the proportion during the 7-day period before baseline used to determine eligibility. Stool consistency is recorded for each bowel movement in the eCOA device, so more than one entry per day may exist. The daily result should be reduced to whether a Type 6 or Type 7 was included on that date.

A subject will be considered a responder only during weeks for which both components indicate improvement. Subjects must have at least 4 evaluable weeks of data as defined in [Section 10.4](#) for each of the instruments used to determine response. Subjects with less than 4 evaluable weeks of assessments available during the treatment period will be considered as non-responders for overall response.

Subjects who have at least 7 evaluable weeks of data and have reported an improvement in their weekly symptoms for  $\geq 50\%$  of the treatment period will be considered overall responders. Subjects who have 4, 5, or 6 evaluable weeks of data must show improvement for  $\geq 60\%$  of the treatment period to be deemed overall responders.

The days for each week will be taken as calendar days from the Day 1 date (randomisation date).

The denominators for the weekly average of Abdominal Pain Intensity, the stool frequency, and the proportion of days per week with at least one Type 6 or 7 will be the number of days with an assessment during the week. The stool frequency will be multiplied by 7 to convert to a stools per week figure. The stool consistency will be multiplied by 100 to convert to a percentage.

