3.2 Endpoints

Primary Efficacy Endpoint

The primary efficacy endpoint is whether the subject is an overall responder.

A subject is an 'overall responder' if they have reported an improvement in their weekly (Cohort specific) symptoms for \geq 50% of the treatment period (4 out of 8 weeks).

	IBS-C	IBS-D	
Primary Endpoint Responder Symptom Definition	Abdominal Pain Intensity Decrease in weekly average of worst abdominal pain in the past 24 hours score of at least 30% compared with baseline	Abdominal Pain Intensity Decrease in weekly average of worst abdominal pain in past 24 hours score of at least 30% compared with baseline	
	And Stool Frequency	and Stool Consistency (BSS)	
	Increase of 1 or more Complete spontaneous bowel movements (CSBM) per week compared with baseline.	Decrease at least 50% in the proportion of days per week with at least one stool that has a consistency of Type 6 or 7 compared with baseline.	

Secondary Efficacy Endpoints

- Subject global assessment of relief
- Stool consistency/frequency
- IBS-QOL
- IBS-SSS
- HADS

Exploratory Endpoints

Safety Endpoints

- Incidence, nature, severity, relatedness, seriousness, expectedness and outcome of adverse events
- Haematology and blood chemistry assessments
- Vital signs

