10.7 Handling of Missing Data

Subjects who do not provide enough data to enable assessment of whether that subject is a responder will be deemed a non-responder.

An 'evaluable week' is one in which there are at least four twenty-four hour (4 day) records of abdominal pain score and at least four daily records of the number of complete spontaneous bowel movements and Bristol stool chart.

If a subject has not provided four evaluable weeks of data, then they are deemed to be a non-responder.

If a subject has provided at least four evaluable weeks of data then they are deemed to be a responder if they have reported an improvement in their weekly symptoms for $\ge 60\%$ of the

evaluable weeks (if the total number of evaluable weeks is four, five or six) or for \geq 50% of the evaluable weeks (if the total number of evaluable weeks is seven or eight).

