#### 4. STUDY DESIGN AND PLAN

This is a randomised, placebo-controlled, parallel group, repeat dose multicentre study in adult male and female subjects of 18 to 70 years of age with a confirmed diagnosis of IBS-C or IBS-D.

The study consists of a Screening Visit, a Baseline Visit (Day 1), an 8-week treatment period with 2 clinic visits, Visit 2 (Week 4) and End of Treatment (Week 8), and a Follow-up Visit 4-6 weeks after the last dose of study medication for a safety check and clinical update.

The Screening Visit is up to 4 weeks before dosing starts. Subjects who fulfill all the eligibility criteria will be provided with an electronic device containing an Electronic Clinical Outcomes Assessment (eCOA) App and will be provided with training and instructions on how to use the device. At this visit, they will complete the IBS-Symptom Severity Score (IBS-SSS) on a device during the clinic visit.

The subjects will be asked to take the device home and complete the following assessments daily over a minimum of a 7-day period prior to attending the clinic for their Baseline Visit 1:

- An abdominal pain intensity rating scale daily
- Bowel movements, Stool consistency/frequency daily and laxative use; if no bowel movements, this should be recorded as zero

The subjects will need to ensure they complete these two assessments at least one day prior to the day of the next clinic visit. The same device will be used throughout the study for all patient reported outcome assessments.

Each subject will be provided with a kit with instructions for the collection of a stool sample. They will be asked to provide a stool sample from the night before or on the morning of the next clinic visit. If necessary, a stool sample may be provided up to 2 days after the Baseline visit provided it is from the night before or from the day it is delivered to the clinic.

At the Baseline visit, the study doctor will review the screening data obtained from the device eCOA app and the subject will be classified into either IBS-C or IBS-D subtypes. Subjects will be randomised to receive either Blautix™ or placebo capsules, with instructions for two (2) capsules to be taken at approximately 12-hour intervals; morning and evening, approximately 30 minutes before meals, giving a total of four (4) capsules per day.

Specific assessments performed at each visit are tabulated in the following Schedule of Assessments and Procedures.

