### 10.4 Handling of Dropouts or Missing Data

In general, missing data will not be imputed. Summary data for observed cases only will be presented.

For weekly assessments derived from daily eCOA data, the weekly values will be considered missing if there are less than 4 days with data assessed within a week.

For the primary endpoint, overall response, subjects must have at least 4 evaluable weeks of data. An evaluable week is one in which there are at least four 24-hour daily records of abdominal pain score, number of CSBMs, and Bristol stool chart. If number of CSBMs for a date is 0, then Bristol stool chart data is expected to be missing. The day will still count towards the 4-day minimum. Subjects with less than 4 evaluable weeks of data will be considered non-responders.

Mixed model repeated measures (MMRM), which provide valid parameter estimates even with some values missing, will be used to analyze continuous assessments taken over time.

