## **13. CHANGES TO PROTOCOL SPECIFIED ANALYSES**

The EE analysis set will not be based on all major protocol deviations as indicated in the protocol, but on a subset of the major deviations that are deemed to have significant impact on efficacy data and will be determined in the data review meeting, prior to database lock and prior to unblinding the study.

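### SAP 10.1.1 takes the 60% responder threshold over the 8-week treatment period, not the evaluable weeks as in protocol 10.7, so subjects with 4, 5 or 6 evaluable weeks need 5 improved weeks instead of 3, 3 or 4

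*SAP*

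**What the plan says.** **SAP 10.1.1** sets two thresholds by number of evaluable weeks. With at least 7, improvement is needed for at least 50% "of the treatment period will be considered overall responders". For fewer weeks: "Subjects who have 4, 5, or 6 evaluable weeks of data must show improvement for" at least 60% "of the treatment period to be deemed overall responders". Subjects with fewer than 4 evaluable weeks are non-responders.

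**Protocol 10.7** has the same groups and percentages but another denominator. Improvement is needed for at least 60% of the "evaluable weeks (if the total number of evaluable weeks is four, five or six) or for" at least 50% of the evaluable weeks when there are seven or eight.

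**Length of the treatment period.** SAP section 4 describes "an 8-week treatment period with 2 clinic visits". Protocol 3.2 uses the phrase in the same sense when it defines an overall responder by improvement for at least 50% "of the treatment period (4 out of 8 weeks").

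**SAP 10.4** repeats the 4-week minimum and adds that "the weekly values will be considered missing if there are less than 4 days with data assessed within a week". It does not restate the responder denominator, so it does not correct 10.1.1.

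**SAP section 13** lists a single departure from the protocol: "The EE analysis set will not be based on all major protocol deviations as indicated in the protocol". The responder denominator is not mentioned.

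**The concern.** The primary endpoint has two written definitions that classify some subjects differently, and the SAP does not acknowledge the difference. Someone with 3 improved weeks out of 4 evaluable weeks is a responder under protocol 10.7 and a non-responder under the SAP.

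The SAP text also sits badly with itself. It sets 4 evaluable weeks as the minimum and names a rule for subjects with 4, yet that rule asks for 5 improved weeks.

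Responder status feeds the primary test in both cohorts, the Efficacy Evaluable sensitivity analysis, the CMH, subgroup and logistic analyses, and the primary efficacy table in the SAP's interim analysis. The stricter rule applies to both arms, so the expected harm is lower response rates and lost power. No inflation of false positives is claimed. Resolving the conflict after the blind is broken would make the choice post hoc under SAP section 6.

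**Working it through.** **1. Week counts.** Minimum improved weeks = ceil(threshold × denominator). Check against the protocol's one worked count: ceil(0.50 × 8) = 4, which matches the 4 of 8 weeks in protocol 3.2.

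| Evaluable weeks | Protocol 10.7 | SAP 10.1.1 as written | SAP count as share of evaluable weeks |
|---|---|---|---|
| 4 | ceil(0.6 × 4) = 3 | ceil(0.6 × 8) = 5 | 125% |
| 5 | ceil(0.6 × 5) = 3 | 5 | 100% |
| 6 | ceil(0.6 × 6) = 4 | 5 | 83% |
| 7 | ceil(0.5 × 7) = 4 | ceil(0.5 × 8) = 4 | 57% |
| 8 | ceil(0.5 × 8) = 4 | 4 | 50% |

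Below 4 evaluable weeks both texts give non-response. The difference is therefore confined to 4, 5 and 6.

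**2. Is 5 of 4 really out of reach?** It is if only evaluable weeks can be improved weeks. SAP 10.4 largely implies this, because a weekly value with fewer than 4 days of data is missing. One gap remains. An evaluable week needs pain, CSBM and Bristol chart records in both cohorts, while each cohort's response uses pain and only one stool measure. A week could fail only on the record its cohort does not use. SAP 10.1.1 does not settle whether such a week can count as improved.

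**3. Plan's power, reproduced.** Inputs from protocol 10.2 and SAP section 5: 125 per arm, 40% against 55%, one-sided alpha 0.10, Pearson test with Yates correction. With x₀, x₁ responders, n = 125, N = 250 and s = x₀ + x₁, reject if x₁ > x₀ and

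z = (|x₁(n − x₀) − x₀(n − x₁)| − N/2) / √(s(N − s)n²/N)

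reaches the 90th normal percentile. Summing the two binomial distributions over all outcomes gives 82.5%, consistent with the stated minimum of 80%.

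**4. Illustrative effect of the SAP wording.** The assumptions, none of them in the documents, are:
- 40% and 55% are the response rates on complete 8-week data.
- Weekly improvement is beta-binomial with within-subject correlation 0.2 to 0.6, its mean solved so that P(at least 4 of 8) = 0.40 or 0.55.
- Affected subjects split equally over 4, 5 and 6 evaluable weeks, and missing weeks are unrelated to response.

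Mean response among affected subjects (correlation 0.2 to 0.6):

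| Arm | Protocol 10.7 | SAP wording | Responders lost per 100 affected |
|---|---|---|---|
| Placebo | 27.6–34.6% | 5.7–15.5% | 21.9 to 19.1 |
| Blautix | 40.2–49.1% | 10.2–23.9% | 30.0 to 25.2 |

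These rates are mixed with the complete-data rates. For a 10% share and correlation 0.2, SAP wording: placebo 0.9 × 40 + 0.1 × 5.7 = 36.6%; Blautix 0.9 × 55 + 0.1 × 10.2 = 50.5%; power 78.8%. The full range per cohort is:

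| Share with 4–6 evaluable weeks | Power, protocol 10.7 | Power, SAP wording |
|---|---|---|
| 5% | 82.0–82.4% | 80.5–81.3% |
| 10% | 81.6–82.3% | 78.8–80.2% |
| 20% | 80.9–82.2% | 75.8–78.4% |

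**The case against.** **It is only loose wording.** A sensible reader may take the treatment period to mean the evaluable weeks within it, and the table specifications, a separate document not seen here, may already do so. This is probably what was intended: a 4-week minimum has no purpose if 4 weeks cannot suffice. But the SAP does not say so, and protocol 3.2 uses the phrase for 8 weeks. The double independent programming in SAP section 6 is no safeguard, since two programmers following the literal text would agree on the wrong count.

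**The SAP may be deliberately stricter.** Five weeks matches neither protocol 10.7 (3, 3, 4) nor protocol 3.2 (4 of 8), and section 13 does not declare it.

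**Protocol 10.7 itself relaxes protocol 3.2.** This stands. With 4 or 5 evaluable weeks, 3 improved weeks suffice under 10.7 but fall short of 4 of 8. In the model above, about 33–51% of the placebo and 29–48% of the Blautix responders lost under the SAP wording have only 3 improved weeks. Measured against a strict 4-of-8 rule, the comparison at a 10% share is 78.8–80.2% (SAP) against 80.6–82.0%, a smaller gap. Still, 10.7 is the specific missing-data rule and, by the protocol's amendment log, was added at the FDA's request. Following it is defensible, and the SAP wording is stricter than either rule.

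**The power figures depend on the model.** This also stands. A harsher assumption, that 5%, 10% or 20% of protocol responders in both arms are in the affected group and all lose responder status, gives 79.6%, 77.1% or 71.8%. The figures illustrate the size; the case rests on the conflicting definitions.

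**Conclusion.** The concern holds: SAP 10.1.1 is wrong as written. It requires 5 improved weeks where protocol 10.7 requires 3, 3 or 4, and it makes response essentially unattainable at the SAP's own minimum of 4 evaluable weeks. This follows from the two texts and needs no modelling.

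The effect on the result is conditional on how many subjects have 4 to 6 evaluable weeks. Under the assumptions in the check, per-cohort power stays just above 80% at a 5% share, is around 80% at 10% and falls below it at 20%. About 19–22 placebo and 25–30 Blautix responders per 100 affected subjects would be reclassified as non-responders.

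It must be fixed because it is an undeclared conflict in the definition of the primary endpoint, whatever the power loss proves to be. How the rule was actually programmed cannot be seen from these documents.

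**What to change.** Before unblinding, in SAP 10.1.1:

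- Change the denominator from the treatment period to the evaluable weeks in both threshold sentences. The edit to the 50% sentence changes no subject's status.
- State that only evaluable weeks can count as improved weeks, which closes the gap about weeks short only on an unused diary record.
- Print the required counts: 3/4, 3/5, 4/6, 4/7, 4/8.
- State that this rule, taken from protocol 10.7, makes the protocol 3.2 definition operational when weeks are missing.

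Protocol Appendix 13 indicates that the primary assessments were complete by March 2020, and SAP 10.5 provides an unblinded interim that includes the primary efficacy table. The correction should therefore be dated relative to that interim and should cite the protocol rule's earlier origin (version 2.0, May 2018), so that it does not look data-driven. The table specifications and program should be checked against the printed counts.

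Optional: a sensitivity analysis requiring at least 4 improved weeks of 8, with non-evaluable weeks counted as not improved.

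Cost: two phrases, two clarifying sentences and a line of counts, plus the dating note and the program check. No protocol amendment, new data or new mandatory table is needed.

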### **10.1.2 Secondary Efficacy Endpoints**

#### **10.1.2.1 Subject Global Assessment of Relief**

The Subject Global Assessment of Relief is collected weekly through the eCOA system. It is a comparison of how the subject has felt over the past week with regards to their IBS to the way they felt before entering the study. It is measured on a 5-point Likert scale with the following responses:

Completely relieved; considerably relieved; somewhat relieved; unchanged; worse.

#### **10.1.2.2 Stool Consistency/Frequency**

Frequency of bowel movements is captured daily by the eCOA system. The consistency of each bowel movement is rated according to images in the 7-level Bristol Stool Chart. See Appendix B for a graphic representation of the chart.

Derivation of the stool frequency per week and the proportion of days per week with an increase of at least one stool with consistency of Type 6 or 7 from baseline, as described as components of the primary efficacy endpoint in [Section 10.1.1](#).

#### **10.1.2.3 IBS Quality of Life Questionnaire**

The IBS Quality of Life (IBS-QOL) questionnaire consists of a series of 34 questions concerning the subject's feelings about their IBS over the past month. The responses to each question are on an ordinal scale and numbered 1-5 with:

- 1 = NOT AT ALL
- 2 = SLIGHTLY
- 3 = MODERATELY
- 4 = QUITE A BIT
- 5 = EXTREMELY or A GREAT DEAL

The possible raw score range for the numerator of the total quantity is 136. The formula transforms the item scores into a 4 to 0 range so that higher values of the total score are associated with increased quality of life. It is possible to derive eight subscale scores as well as a single global score. Each item is taken to contribute equally to each subscale with each subscales containing the following items:

| Subscale                   | IBS-QOL Question Numbers       | Possible Raw Score Range |
|----------------------------|--------------------------------|--------------------------|
| Dysphoria                  | 01, 06, 07, 09, 10, 13, 16, 30 | 32                       |
| Interference with Activity | 03, 18, 19, 22, 27, 29, 31     | 28                       |
| Body Image                 | 05, 21, 25, 26                 | 16                       |
| Health Worry               | 04, 15, 32                     | 12                       |
| Food Avoidance             | 11, 23, 28                     | 12                       |
| Social Reaction            | 02, 14, 17, 34                 | 16                       |
| Sexual                     | 12, 20                         | 8                        |
| Relationships              | 08, 24, 33                     | 12                       |

Subscales are scored through simple summative scaling. All items are negatively framed with the greatest response scale equaling the worst quality of life. When scored, all items are reversed so that as IBS-QOL scores increase, quality of life increases. All final raw scores are transformed to a 0 to 100 scale using the following formula: 
$$\frac{\text{Sum of the items} - \text{lowest possible score}}{\text{Possible raw score range}} * 100$$

This transformation converts the lowest and highest possible scores to zero and 100, respectively. Scores between these values represent the percentage of the total possible score achieved. The IBS-QOL instrument and scoring programs have used this transformation to provide comparative data for interpretation.

